7.5 Early Termination Visit

If subjects discontinue from the study, they may be asked to make an early termination visit. At the time of the early termination visit, the reason for early termination will be recorded, current health status since the last visit will be reviewed, and all concomitant medications will be recorded. A targeted physical examination may be performed, as indicated, and information regarding AEs will be solicited. Any ongoing related AEs will be followed to resolution or until a stable chronic condition has been established. If subjects do not wish to present for an early termination visit, reasons for study termination will be solicited by phone when possible.

7.6 Unscheduled Visit

Unscheduled visits may occur at any time during the study. These visits may either be a clinic visit or a home visit. Depending on the nature of the visit, activities will include a review of the medical history including concomitant medications, assessment of adverse effects or other illnesses, vital signs, a targeted physical examination as necessary, and any additional testing deemed necessary.

7.7 Compensation for Participation

Subjects will be compensated for the time and effort of participation per local IRB requirements.

8 STUDY PROCEDURES AND EVALUATIONS

8.1 Clinical Evaluations

Medical History: Study personnel will take the medical history of all subjects. This history will include significant medical disorders of the head, eyes, ears, nose, throat, mouth, cardiovascular system, lungs, gastrointestinal tract, liver, pancreas, kidney, nervous system, blood, lymph glands, endocrine system, musculoskeletal system, skin, and genital/reproductive tract. It will also include a history of allergies, cancer, immunodeficiency, psychiatric illness, substance abuse, and autoimmune disease. Patients will also be queried regarding any previous influenza vaccinations, the date and source of vaccine, and the type of vaccine administered. Each subject's NYSIIS record will also be accessed to assess for vaccination history by study personnel.

Medication History: Study personnel will record all medications, including prescription and over-the-counter drugs (such as vitamins, minerals, supplements, homeopathic preparations and/or therapies), taken by the subject in the 30 days prior to enrollment.

Targeted Physical Examination: Licensed study clinicians (i.e., physician, physician's assistant, and study nurses) will obtain a subject's weight and vital signs (respiratory rate, pulse, and temperature) and a targeted physical examination will be conducted if necessary. This targeted physical examination will focus on the respiratory system and the cardiovascular system. In subjects enrolled through the ED, this information may be obtained through a review of the medical record.

8.2 Laboratory Evaluations/Assays

8.2.1 Specimen Collection, Preparation, Handling and Shipping

Blood draw: A weight-based sample of whole blood will be collected, if able, by venous, with the blood volume determined as described in Table 1. This sample will then be transferred to appropriate-sized tubes containing heparin or sodium citrate. If blood is available, a sample of fresh blood in sodium citrate tubes will be shipped to our collaborators at University of Chicago overnight using appropriate biosafety precautions to enable quantification, isolation, and determination of the BCR repertoire of plasmablasts. All other blood will be centrifuged and plasma and PBMCs will be isolated within several hours of the blood being obtained (blood is stable in heparinized tubes for at least 6 hours post draw). Plasma will be aliquoted and stored in an Ultra Low Temp Freezer at $\leq -70^{\circ}\text{C}$ for use in ELISA, antibody array, and microneutralization assays. PBMCs will be washed, counted, and frozen in liquid nitrogen for later use in intracellular cytokine staining, multiplex cytokine assays, RNA-seq, and CD4 T cell and memory B cell Elispot assays, with a subset of PBMCs sent to our collaborators NIAID for further analysis. If blood cannot be successfully obtained, this will be documented on the enrollment or case report form as "unable to be obtained." In the event that the child is unwilling to cooperate with research staff or attempts to draw blood are unsuccessful, the research staff may forego further intervention procedures for the given study visit. If the child and parent/LAR

are willing to participate further, then follow up visits will be scheduled and attempted as outlined in the timeline.

All blood will be drawn by experienced and trained pediatric nurses or physicians, with pain minimized through comforting and distraction techniques. Only the minimum amount of blood necessary to achieve the study objectives will be obtained, with the blood volume being within a level accepted as safe (Table 1). As a child's total blood volume is related to body weight, we have chosen a weight based approach to determine the maximum volume of blood to be obtained. This will allow us to optimize our likelihood of being able to accomplish the study objectives while still prioritizing the safety of the child. Current policy suggests that blood volume limits between 1% and 5% of the total blood volume on a single draw and up to 10% of total blood volume over an 8 week period will present minimal risk to children [31]. A child's total blood volume estimated at around 80 mL/kg. The proposed blood draws in this protocol impose a maximum upper limit of 1 mL/kg on any single draw (about 1.25% of estimated TBV), with a maximum of 3 mL/kg (about 3.75% of estimated TBV) over any 8 week period for pediatric patients. This volume remains well below the upper limit of 10% of total blood volume in an 8 week period and is consistent with the available evidence on what will present minimal risk to children while still providing enough PBMCs to perform the in depth analysis of CD4 T cell and B cell specificity and functional capacity and evaluation of antibody responses required for this study.

Study Year 1					Study Year 2/3				Total	
Body Weight (kg)	Blood volume visit 1 (mL)	Blood volume visit 2 (mL)	Blood volume visit 3 (mL)	Max/8 weeks (mL)	Blood Volume Visit 4, 7 (mL)	Blood Volume Visit 5, 8 (mL)	Blood Volume Visit 6, 9 (mL)	Max/8 weeks (mL)	mL/kg per draw	Max % of TBV (over 8 weeks)
2-4	2	2	2	6	2	2	2	6	1	3.75%
≥5-10	4	4	4	12	4	4	4	12	0.8	3%
≥11-15	8	8	8	24	8	8	8	24	0.73	2.7%
≥16-20	12	12	12	36	12	12	12	36	0.75	2.8%
≥21-30	16	16	16	48	16	16	16	48	0.76	2.8%
≥31-40	20	20	20	60	20	20	20	60	0.64	2.4%
≥41-50	30	30	30	90	30	30	30	90	0.73	2.7%
≥51-60	40	40	40	120	40	40	40	120	0.78	2.9%
≥61	50	50	50	150	50	50	50	150	0.82	3%

Nasal swab: Nasal swabs will be obtained by placing two UV-sterilized soft nylon flocked swabs into alternate nostrils of the subject and gently rotating them across the mucosa to collect respiratory secretions. When appropriate, one of these swabs will be used to perform a rapid influenza test in the primary care office, URM or RGH ED, the VRU, or the subject's home.

The other swab will be placed into 1 mL of viral culture transport media for RT-PCR studies and stored in an Ultra Low Temp Freezer at $\leq -70^{\circ}\text{C}$.

Nasal wash: Between 1.5 and 5 mL of sterile saline will be instilled and collected, if able, by gentle suction with a flexible catheter or bulb syringe inserted approximately 5 cm into the naris. Alternatively, we may opt to instill the entire volume into a single nostril, as this is considered safe and the anticipation of the 2nd nasal wash has been significantly distressing to some children [34]. In the event that the child is unwilling to cooperate with research staff or attempts to collect the nasal wash are unsuccessful, the research staff may forego further intervention procedures for the given study visit. If the child and parent/LAR are willing to participate further, then follow up visits will be scheduled and attempted as outlined in the timeline. Within several hours, the nasal wash fluid will be centrifuged to pellet the cells and the supernatant will be removed and stored in an Ultra Low Temp Freezer at $\leq -70^{\circ}\text{C}$. The cell pellet will be washed, after which any cells obtained will be counted and frozen in liquid nitrogen for later analysis.

Nasal Brush: A UV-sterilized pediatric flocked swab will be used to collect inferior turbinate nasal epithelial cells for genome-wide expression analysis. The brush specimen will be obtained, if able, immediately following the NW in order to obtain mucosal lining cells free of mucus and lymphocytes. The swab will be placed in the nostril and rotated with an up and down motion gently against the lining mucosa for ~ 5 seconds. The swab will then be placed into 2 mL of RNeasy Protect (Qiagen) and transported to the lab for RNA isolation, which will be completed within a 1 week time period. Recovered RNA will be stored in an Ultra Low Temp Freezer at $\leq -70^{\circ}\text{C}$ until use.

8.2.2 Laboratory Evaluations

Detection and quantification of influenza virus: Influenza will be detected from potentially infected subjects by (1) rapid antigen testing using a commercial assay (BinaxNOW, Alere, Waltham, MA or QuickVue Influenza A+B test, Quidel, San Diego, CA) and (2) real time RT-PCR using primers obtained from BEI Resources (Manassas, VA) or using the ABI 7500 real-time PCR platform. Two UV-sterilized soft nylon flocked swabs will be used to collect nasal swab samples from subjects potentially infected with influenza. One swab will be used for rapid antigen detection on site, while the other will be placed into 1 mL of viral culture transport media for use in real time RT-PCR to detect and quantify influenza viral load. This sample will be stored and may be used to sequence the infecting influenza virus at a later time point.

Multiparameter flow cytometry: PBMCs will be thawed, rested overnight, and, when appropriate, stimulated with influenza-specific peptide pools as experimental antigens, Staphylococcal enterotoxin B (a superantigen) as a positive control, or a pool of irrelevant peptides from the Sin Nombre virus glycoprotein precursor protein or media alone as a negative control for 10-20 hours, with Brefeldin A and monensin added to inhibit cytokine secretion for the final 8 hours of incubation. Cells will then be stained with a viability marker and a panel of antibodies against surface markers. When appropriate, they will then be fixed, permeabilized, and stained intracellularly using antibodies against cytokines as well as other markers. All events will be collected on a flow cytometer within the University of Rochester Medical Center Flow Core. We have the flexibility to adjust and modify these panels as necessary to optimize

our staining results.

Multiplex cytokine assay: Multiplex cytokine assays will be used to determine the antigen-specific cytokine production potential of the total CD4 T cell population. Cells will be thawed, rested overnight, and depleted of CD8 and NK cells. They then will be stimulated with HA and NP peptide pools or irrelevant peptides as a negative control. Following around 48 hours of coculture, supernatants will be assayed for levels of 30 common cytokines and chemokines with a human cytokine/chemokine magnetic bead panel (Bio-Rad Laboratories, Hercules, CA) and analyzed on a Bio-Plex200 system.

Peptide-specific CD4 T cell Elispot: IFN γ , IL-2, and granzyme B Elispot analysis of human PBMCs will be performed by established assays. Briefly, PBMC will be thawed, rested overnight, and depleted of CD8 and NK cells. They then will be cultured for 16-48 hours in Millipore 96-well PVDF plates coated with capture antibodies for either IFN Elispot analysis of human PBMCs will be performed by established assays. Briefly, PBMC will be thawed, rested overnight, and depleted

Detection of memory B cells: With collaborators at the University of Rochester, the method of Crotty and colleagues [35] will be adapted to determine frequencies of influenza-specific memory B cells. Cultured cells will be non-specifically stimulated by a mixture of mitogens, followed by HA, NP, and Ig Elispots for determination of (i) antigen-specific IgG ASC frequencies, and (ii) total IgG ASC frequencies. Antigen-specific MBC frequencies will be expressed as the percentage of antigen-specific IgG ASC/total IgG ASC.

RNA-seq: Total RNA will be extracted from PBMCs. This RNA will then be provided to the genomics core for construction of a cDNA library and high-throughput sequencing using an Illumina HiSeq 2500 System, with 20 million reads per sample to allow unbiased evaluation of whether the overall pattern of gene expression is influenced by a subject's prior influenza exposure.

Evaluation for cross reactive HA antibody by array: With collaborators at the University of Rochester, dilutions of serum will be applied to a chip coated with multiple HA proteins in microarray format [36] or evaluated using a Luminex-based technology [37] to rapidly quantify antibody levels against multiple HA proteins

Microneutralization assays: MDCK cells will be grown to confluence in a 96 well plate. Serial dilutions of serum will be preincubated with virus and transferred to MDCK cells to allow unneutralized virus to infect the cells. Free virus is then washed away and the plate is incubated to allow cytopathic effect to occur. The antibody titer is the highest serum dilution able to prevent MDCK cell infection.

ELISA: Plates will be coated with HA or NP protein and then incubated with dilutions of serum. After washing and blocking nonspecific binding, plates are incubated with a horseradish peroxidase-conjugated goat anti-human IgG antibody and developed with 3,3',5,5'-tetramethylbenzidine dihydrochloride substrate with absorbance read at 450 nm. To determine antibody avidity, sera are incubated on a recombinant HA-coated plate in the presence of serial

dilutions of sodium thiocyanate. The serum avidity is defined as the concentration of sodium thiocyanate that induces 50% inhibition of antibody binding.

Surface Plasmon Resonance (SPR): SPR measures the off rate (rate at which antibodies dissociate from the antigen) of antibody-antigen binding. The off rates provide a measure of how well the antibodies bind, indicating their quality. In an ideal immune response to vaccine, the off rates should go down, indicating an improved recognition of antigen. For these studies, collaborators at the FDA will use recombinant influenza hemagglutinins that match that year's vaccine formulation, as well as HA head only and HA stalk only recombinant proteins to measure antibody off rates.

Isolation of Influenza-Specific Monoclonal Antibodies: We will send fresh blood samples to the University of Chicago at the baseline visit and days 8+2 and 24 +/- 4 days post-vaccination or infection in study years 1 and 2 and plasmablasts (day 8) and antigen-specific memory B cells (day 24) will be isolated by flow cytometry. Monoclonal antibodies will be expressed from the cloned variable genes of single cells and the antibodies and serum will be tested for binding, neutralization, and epitope specificity. In addition, BCR repertoire will be determined using the 10x genomics platform.

Systems Biology Approaches: We will be sending PBMCs to the NIAID Systems Genomics and Bioinformatics Unit to better understand immune development in childhood. Using a combination of approaches including flow cytometry, an analysis of cellular transcriptional activity in immune cell subset and single cells as analyzed by RNA-seq or microarrays, PBMC transcriptome analysis, and additional 'omics' assays for assessing immune receptor repertoires including TCR and BCR profiling, the state of the immune system both at baseline and following immune perturbations will be assessed.

Instructions for specimen preparation, handling, and storage are described in local SOPs.

8.3 Procedures to be Followed in the Event of Abnormal Laboratory Test Values or Abnormal Clinical Findings

Subjects will be informed of the results of their rapid influenza tests, together with a disclaimer that the sensitivity of this test is limited. Subjects will be notified that any repeat testing or treatment, if indicated, can be provided by their primary care physician.

If a subject tests positive for influenza by PCR testing they will be contacted to assess for interest in full study participation. This testing result will not be available real-time and will not be provided to primary care physicians as this test is not CLIA certified.

Subjects developing signs and symptoms of influenza during subsequent monitoring will be referred to an appropriate health care provider for evaluation and treatment, if indicated. If severe illness symptoms develop, subjects will be referred to their pediatrician or the pediatric emergency department per local SOP.

9 ASSESSMENT OF SAFETY

9.1 Specification of Safety Parameters

An FDA approved, licensed seasonal inactivated influenza vaccine will be administered in this protocol as per standard of care during influenza vaccine season following the manufacturers' instructions and safety precautions.

As **Quadrivalent Fluzone** is a licensed vaccine, NIAID does not expect that any new vaccine related safety signal will be detected in this trial. Therefore, the only adverse events reported to DMID will be adverse events that are reportable to Vaccine Adverse Event Reporting System (VAERS).

The National Childhood Vaccine Injury Act (NCVIA) **requires** healthcare providers to report to VAERS:

- Any adverse event listed by the vaccine manufacturer as a contraindication to further doses of the vaccine; and/or
- Any adverse event listed in the VAERS Table of Reportable Events Following Vaccination that occurs within the specified time period after vaccination (see below).
 - Anaphylaxis or anaphylactic shock (7 days)
 - Shoulder Injury Related to Vaccine Administration (7 days)
 - Vasovagal syncope (7 days), not related to blood draws
 - Guillain-Barré Syndrome (42 days)
 - Any acute complication or sequelae (including death) of above events (interval - not applicable)

Upon reporting to VAERS, any such report will also be provided to the DMID Medical Officer, DMID Clinical Project Manager, and local IRB as required. A paper copy of this information will be filed in the subject's chart and the information will be inputted into BLIS as an VAERS-reportable adverse event.

In addition, CDC encourages reporting any serious, unexpected (not listed in product label or Investigator's Brochure) or suspected adverse reaction to influenza vaccination to VAERS, with a copy of any such reports provided to the DMID Medical Officer, DMID Clinical Project Manager and local IRB as required.

Data on intermittent illnesses, hospitalizations, surgeries and other events that are unrelated to the study intervention but that may impact the health of the child will be collected from the first study visit to study conclusion, as these events may effect the immunologic endpoints of the study. This will include data on upper respiratory infections, febrile illnesses, common childhood procedures such as PE tube placement or tonsillectomy & adenoidectomy, and similar data. Collected information will include details on approximate date of onset, approximate date of resolution (if known), severity, whether the event was associated with respiratory symptoms or fever, and outcome; relatedness to vaccine will not be captured as these events are expected to

be unrelated to the vaccine. This information will be recorded on an illness/other event CRF and in Blis following adoption of Protocol v9. Although data on these illnesses/other events will be collected, this data will not be reported to DMID as Fluzone is a licensed vaccine and DMID does not expect any new vaccination safety signals to be detected as a result of this study.

10 CLINICAL MONITORING

The purpose of clinical monitoring is to protect the rights and well-being of human subjects in this study; to ensure that data are accurate, complete and verifiable from source documents; to ensure that conduct is in compliance with the currently approved protocol/amendments, with Good Clinical Practice, and with regulatory requirements.

10.1 Site Monitoring Plan

Site monitoring will be conducted using the DMID tools provided to ensure that human subject protection, study procedures, laboratory procedures, and data collection processes are of high quality and meet sponsor, GCP/ICH, and regulatory guidelines, and that the study is conducted in accordance with the protocol and sponsor standard operating procedures. DMID, the sponsoring agency, or its designee will conduct site-monitoring visits as defined in the site monitoring plan.

Site visits may be made at standard intervals as defined by DMID and may be made more frequently as directed by DMID. Monitoring visits will include, but are not limited to, review of regulatory files, sample tracking log, CRFs, informed consent forms, medical and laboratory reports, and protocol compliance. Study monitors will meet with investigators to discuss any problems and actions to be taken and document visit findings and discussions. The University of Rochester's IRB and other regulatory agencies may also conduct study monitoring visits.

11 STATISTICAL CONSIDERATIONS

11.1 Study Hypothesis

The primary hypothesis being tested in this study is that there will be differences in the specificity, magnitude and functionality of CD4 T cell and B cell reactivity in a cohort of young children depending on early childhood exposures.

11.2 Sample Size Considerations

Because the degree of variability in many of the measurements in this study are unknown, estimating with precision the correlation of patient characteristics (age and prior vaccination history) with outcomes (CD4 T cell response magnitude and function, antibody quality and quantity and B cell response) is not possible. The study will evaluate these outcomes and, if trends towards a relationship are discovered, subsequent studies will evaluate these in more detail.

11.3 Planned Interim Analyses (if applicable)

No formal interim analysis is planned. However, assay results will be reviewed as they become available

11.3.1 Safety Review

N/A, no interim analysis of safety is planned.

11.3.2 Immunogenicity or Efficacy Review

N/A, no interim analysis of safety is planned.

11.4 Final Analysis Plan

Data will be analyzed at the end of the study, with results available for publication at that time.

A cohort of n=20 to 60 healthy children that receive a prime-boost vaccination with IIV and n=20 children infected with influenza acutely will be recruited for each age cohort. Their T cell and antibody responses will be measured at three time points: baseline, day 8, and day 24 post-vaccination. We will apply Shapiro-Wilk's test to check the normality. If the data passes the normality test, two sample *t*-tests will be used to detect significant mean difference between the children of different ages and flu exposures at each time point. Otherwise, Wilcoxon rank-sum test will be used. For follow up visits, subjects will be followed longitudinally for one to two years with yearly revaccination with IIV. CD4 T cell responses (flow cytometry) and B cell and antibody responses will be measured at three time points: prior to IIV re-vaccination, 8 and 24 days post re-vaccination. We will apply one-way ANOVA *F*-test (or Kruskal-Wallis test, if the

normality assumption is rejected) to detect significant group differences at each time point. Because multiple response variables are used in this analysis, the p -values will be adjusted by the Benjamini-Hochberg multiple testing procedure [38] to control the false discovery rate (FDR) at the level of 0.05.

General linear models of difference or fold change in T/B cell response at following time points from baseline will be used to explore how childhood exposures affect immune responses over time, while controlling potentially confounding variables including age, sex, presence of asthma or allergies, or other acute or chronic illnesses and medications that may impact the immune response. In addition to time-specific comparisons, the following linear mixed effect model will be used to analyze data collected from all time points

$$y_{kit} = \alpha_k + \beta_{1k}G(i) + \beta_{2k}X_{kit} + \gamma_{kt} + \dot{\mathbf{0}}_{kit}. \quad (0.1)$$

Here y_{kit} represents the k th response variable measured from the i th subject at the t th time point; α_k is the overall mean value of y_{kit} ; $G(i)$ is a binary variable which equals 0 if the i th subject is vaccinated with IIV and 1 otherwise; β_{1k} is a linear coefficient that quantifies the magnitude of the group-effect; β_{2k} are linear coefficients for potentially confounding clinical variables listed above; γ_{kt} is a random effect term that quantifies the time effects; and $\dot{\mathbf{0}}_{kit}$ represents independent measurement errors. Likelihood ratio test will be used to test $H_0 : \beta_k = 0$ against $H_1 : \beta_k \neq 0$.

In case of high-dimensional data in different scales, standardization will be applied before model fitting and variable selection. Variable selection approaches using AIC or BIC criteria will be used to select the significant predictors. Penalized-based variable selection procedures such as LASSO [39] or SCAD [40,41] may be used to overcome the drawbacks of ad-hoc methods of stepwise, best subset selection, etc. post-hoc.

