2.2 Scientific Rationale

This protocol is a population-based study that will address the hypothesis that vaccination and infection differentially drive both the CD4 T cell and B cell immunity. Recent data in the literature [3,4,28], and our own preliminary data suggest that initial encounters with influenza have a long lasting effect on both CD4 T cell and B cell mediated immunity. This protocol will address how early immunity against influenza virus is primed by vaccination versus infection and whether this differentially poises subsequent immune responses on re-challenge with influenza vaccination. We will specifically test whether the more robust pro-inflammatory response initiated on first exposure to a natural influenza infection promotes imprinting of both CD4 T cell and B cell responses, influencing long term specificity and functionality. We also will examine the effects of age and exposure on the immune response that develops following influenza vaccination. To do this, we will first examine whether early exposure to a live viral infection compared to vaccination leads to a distinct phenotype and specificity in both the B cell and CD4 T cell compartments. Subsequently, we will determine whether the CD4 T cell repertoire is remodeled over time by examining CD4 T cell specificity, cytokine production, and expression of markers and transcriptional factors associated with a negative regulatory CD4 T cell phenotype in children of different ages versus adults.

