3.2 Outcome Measures

3.2.1 Primary Outcome Measures

- Assess the frequency and functional potential of CD4 T cell responses on a single cell level using full spectrum flow cytometry following either infection or inactivated influenza vaccine administration, with stratification by age and exposure history

[figure not shown]

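### Section 11.4 defines no relative CD4 variable and no group-by-antigen or group-by-subset contrast, so a general difference in magnitude can be read as a difference in specificity or functionality

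*Combined protocol and SAP*

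**What the plan says.** The primary hypothesis (section 11.1) is that, depending on early exposures, "there will be differences in the specificity, magnitude and functionality of CD4 T cell and B cell reactivity". Section 2.2 asks whether infection rather than vaccination "leads to a distinct phenotype and specificity in both the B cell and CD4 T cell compartments". The primary outcome (section 3.2.1) is the "frequency and functional potential of CD4 T cell responses on a single cell level using full spectrum flow cytometry".

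Section 11.4 provides:

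- two-sample t-tests, or Wilcoxon rank-sum tests, which "will be used to detect significant mean difference between the children of different ages and flu exposures at each time point";
- one-way ANOVA or Kruskal-Wallis tests at each time point after revaccination;
- general linear models of difference or fold change from baseline;
- a mixed model (0.1) in which every coefficient carries the response index k, with one group coefficient per response.

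Multiplicity is handled by Benjamini-Hochberg: "Because multiple response variables are used in this analysis", p-values are adjusted to "control the false discovery rate (FDR) at the level of 0.05".

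On the assays, section 8.2.2 says of the multiplex cytokine assay: "They then will be stimulated with HA and NP peptide pools or irrelevant peptides as a negative control". The flow cytometry paragraph mentions influenza-specific peptide pools without naming the antigens.

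**The concern.** Magnitude is how much a child responds. Specificity is how that response divides between antigens, and functionality is how the responding cells divide between cytokine combinations. The last two are properties of the division within a child, and a higher total raises every component without changing the division.

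The plan compares levels between groups. A result that is significant for HA and not for NP is not a test that the group effect differs between them. A higher frequency of one cytokine subset may only reflect a higher total.

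This matters because the rationale turns on the distinction. Section 2.1 notes that IIV contains only small amounts of internal proteins such as NP, so a different antigen balance after infection is a natural expectation. Section 11.2 says that trends found here will be taken into later studies. A magnitude difference labelled as specificity would send those studies after the wrong question.

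**Working it through.** **1. What is tested.** The plan has no power or error-rate figure to reproduce (section 11.2 says variability is unknown). In the notation of model (0.1), it tests, for each response k, that the group coefficient is zero. A specificity question needs a different null hypothesis: that the group coefficient for NP equals that for HA. No test in section 11.4 addresses it:

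| Element of 11.4 | What it does | Compares antigens or subsets within a child? |
|---|---|---|
| t / Wilcoxon, ANOVA / Kruskal-Wallis | group level, one response, one time | No |
| Difference or fold change | scales a response to its own baseline | No |
| Model (0.1) | one group coefficient per k | No |
| Benjamini-Hochberg | false discoveries across responses | No |
| AIC/BIC, LASSO, SCAD | selects predictors | No |

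**2. Inputs.** From the documents: 30 vaccinated and 20 infected children (cohorts 3 and 4, section 5); other vaccination cohorts have 20 or 60; FDR 0.05. Assumed, because the documents give no values: ln-scale SD 1, within-child correlation ρ between two antigens of 0.4 to 0.8, a two-fold difference, Wilcoxon tests.

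**3. Uniform two-fold difference, same profile, 30 v 20.** Both antigens shift by ln 2 = 0.693. The log ratio shifts by 0.693 − 0.693 = 0. Each single-antigen test has about 63% power. If the two tests were independent, exactly one would be significant in 2 × 0.63 × 0.37 = 47% of studies; positive correlation lowers this. Benjamini-Hochberg lowers it further, since a lone p-value below 0.05 must then be at most 0.05/2 = 0.025.

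| Result | Share of simulated studies |
|---|---|
| Exactly one antigen significant, unadjusted | 20-37% |
| Exactly one antigen significant, with Benjamini-Hochberg | 12-28% |
| Within-child log-ratio test significant | about 5% |

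The higher values go with the lower correlations.

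**4. More responses.** Six responses, the same shift of 0.5 or 0.8 SD in all, correlation 0.3 or 0.6, t-tests with Benjamini-Hochberg: some but not all are significant in 29-67% of runs across 20, 30 or 60 v 20. A multivariate profile test on centred log ratios rejects in 4.6-5.7%. Separate t-tests with Benjamini-Hochberg on the centred responses reject in 4.7-6.0%.

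**5. Functional subsets.** Seven subsets, identical profile, two-fold total (total ln SD 1, subset ln SD 0.5): after Benjamini-Hochberg at least one subset frequency differs in 44% (20 v 20) to 62% (60 v 20) of runs; subset shares differ in about 5%.

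**6. Does the contrast gain power?** The SD of the log ratio is √(2(1 − ρ)): √1.2 = 1.095 at ρ = 0.4, √0.8 = 0.894 at 0.6.

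- NP doubled, HA unchanged: the standardised ratio effect is 0.693/1.095 = 0.63 at ρ = 0.4 and 0.693/0.894 = 0.78 at 0.6, against 0.69 for NP alone. Simulated power at 30 v 20 is 55% and 72% for the ratio, against 63% for the NP test. Break-even is at ρ = 0.5, where √(2 × 0.5) = 1.
- NP × 1.5 and HA ÷ 1.5: the ratio shifts by 2 × 0.405 = 0.81. At least one single-antigen test is significant (unadjusted) in about 50%, and the log-ratio test in 67-99%.

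**The case against.** The strongest reply is that this is an endpoint-definition gap, not a wrong choice of test. The index k in model (0.1) is generic, and nothing stops it from standing for an NP:HA ratio or a subset share; step 4 shows that separate tests on relative variables behave properly. That stands: testing responses one at a time is not itself the fault. But no such variable is defined for CD4 cells, so the plan followed as written never reaches the question.

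A reader might infer that the planned tests have inflated error. They do not. In steps 3 to 5 the groups truly differ on every raw response, so each rejection is correct. The error arises only if a patchy pattern is read as a profile difference, and the documents nowhere state that they will read it so.

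A reader might also infer that specificity and quality go unmeasured throughout. Sections 8.2.2 and 3.2.2 do not support that. Thiocyanate avidity, SPR off rates (including HA head and stalk proteins), epitope specificity of monoclonal antibodies and memory B cells as a percentage of total IgG ASC are already quality or relative measures. None covers CD4 cells, and the memory B-cell percentage does not compare influenza antigens with each other.

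Two further limits stand. The HA and NP pools are named for the multiplex assay, which measures bulk supernatant, and not for flow cytometry, so one assay may not supply both contrasts. And the primary outcome names frequency and functional potential; specificity enters through the hypothesis and rationale.

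The exploratory framing in section 11.2 explains the missing power calculation. It does not explain a named part of the hypothesis that has no matching test.

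**Conclusion.** The point holds for CD4 responses. Section 11.4 contains no valid test of a difference in CD4 specificity, and it defines no share-type variable for functionality. Under a uniform two-fold difference with 30 v 20 children, the pattern most easily mistaken for a specificity difference appears in about 12-28% of studies after Benjamini-Hochberg, against about 5% for a within-child contrast.

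This rests on ln-scale SD 1, two antigens and correlations of 0.4 to 0.8, none of which the documents give. The direction is firm; the percentages are illustrative.

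Two stronger conclusions are not supported: that the plan could never separate these properties, and that a within-child contrast is always more powerful. The contrast answers the right question; whether it gains power depends on the shift and the within-child correlation.

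**What to change.** In section 11.4, keep the per-response tests and assign them to magnitude, with the total background-subtracted influenza-specific response as the summary. Add:

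1. **Specificity:** an arm-by-antigen interaction in a mixed model that stacks the antigen-pool responses from the same assay, with a random effect for child. Name the assay and the pools.
2. **Functionality:** a comparison of the share of responding CD4 cells in each cytokine combination, from flow cytometry.

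State that claims of a different specificity or functionality rest on (1) and (2), and not on which single responses reach significance.

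The cost is plan wording and modest extra analysis; no visits, blood or assays are added if the named assay uses separate antigen pools. The downside is real: ratios and shares are unstable or undefined when few cells respond, as is likely at baseline and in cohort 1A, which is chosen to be unexposed. Use a count-based model, or set a minimum number of responding cells in advance, and report how many children are excluded by cohort.
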